### 10.8.1. Rate of Attacks

The primary endpoint, confirmed attack rate, is the total number of (count) confirmed attacks during the treatment period and standardized to an appropriate denominator, e.g. 7 days for a weekly attack rate. The weekly attack rate will be calculated for each subject:

$$\text{Weekly Attack Rate} = \frac{\text{Number of Attacks} * 7}{\text{Duration (days)}}$$

Number of attacks is total count of attacks reported during the respective dosing period (“Duration (days)” in the above equation]. The primary endpoint will be calculated for the entire dosing period and for the effective dosing period. The weekly attack rate will also be derived for all subject reported attacks and for confirmed attacks requiring treatment.

The attack rates will also be calculated for pre and post treatment periods:

Attack Rate from Screening to Baseline:

$$= \frac{\text{Total Number of attacks reported} * 7}{\text{Duration of the reporting period in days}}$$

Attacks with a start date after screening and before the date of first dose will be included and the duration of the reporting period is date of first dose – date of screening visit+1.

Attack Rate from date of day 29 to the last follow-up on study:

$$\frac{\text{Total Number of attacks reported} * 7}{\text{Duration of the reporting period period in days}}$$

Attacks that start greater than 24 hours after the last dose will be included. The duration of the reporting period is from the date of last dose+24 hours to the date of last follow-up.

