### **11.2.2. HAE Attack and Dosing Diaries**

The Sponsor will supply paper diaries to all sites. Sites will dispense diaries to subjects at screening, Day 1, Day 14 and Day 29. Diaries will be collected on Day 1, Day 14, Day 29 and at follow-up.

At the Screening visit, subjects will be instructed how to complete the diary for an attack. While a subject has a diary in their possession, the subject will fill out the HAE attack diary daily, recalling whether symptoms of an HAE attack were experienced in the last 24 hours. Subjects must fill out the diary daily, regardless of the presence of HAE symptoms. If the subject does report an attack in their diary, additional details about the attack will be required, including location of the symptoms of the attack, severity, and treatment(s) administered and times of administration. During the treatment period, subjects will also record the time of day study drug was taken, and the number of capsules of study drug taken at each dose in the diary on a daily basis. Study drug doses administered in the clinic will be entered into the diary on site.

The Investigator (or designee) will proactively assess completion of the diary, during visits on Days 1, 7, 14, 21 and 29. While study staff are not permitted to make any entries into the diary, subjects may be asked to rectify incomplete diary entries made since the last visit/phone call based on outstanding questions a subject may have or incorrect assumptions/interpretation of diary questions.

Further training on completing the diary should be provided at each clinic visit or where required, during a telephone call.

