#### **10.8. Derived Attack Endpoints**

Subject-reported attacks will be adjudicated by the independent Clinical Endpoint Adjudication Panel (CEAP). The attacks that have been confirmed by the adjudication committee will be included in efficacy analyses. The details of adjudication are provided in the CEAP charter.

The attack endpoints described in this section are based on confirmed attacks by the CEAP, however the rate of attacks will also be calculated for all subject reported attacks. Efficacy analyses will be conducted for HAE attacks reported over the entire dosing period (Days 1 to 28

inclusive), during the dosing period in which BCX7353 should be at steady-state conditions (Days 8 to 28, inclusive), and during the entire study period (Day 1 to the last HAE diary in the follow-up period).

The efficacy analyses will be calculated for 3 treatment periods:

- Entire Dosing Period  
Duration (days) = 28 or (Date of last dose –date of first dose+1), whichever is earlier
- Effective Dosing Period  
Duration (days) = 21 or (Date of last dose –date of first dose-6), whichever is earlier
- Entire Study Period  
Duration (days) = Date of last HAE Attack Diary collection during the follow-up –date of first dose

All efficacy analyses will also be run by treatment period and population (FAS or PP).

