### **10.8.2. Number and Percentage of Subjects Who Are Attack Free**

The following attack free endpoints will be derived for each treatment period (the entire dosing period, and the effective dosing period ):

- The number and percentage of subjects who report no attacks during the treatment period for the FAS set and PP population. Subjects who report no attacks and discontinued before the end of the planned treatment period (day 28) are considered attack free.
- The number and percentage of subjects who report no attacks during the treatment period for the FAS set and PP population excluding subjects who discontinue before the planned treatment period (day 28).
- The number and percentage of subjects who report no attacks during the treatment period for the FAS set and PP population. Subjects who discontinue before the planned treatment period (day 28) are considered not attack free.

The above attack free endpoints will also be derived for the entire study period.

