#### 1. Attack Rate based on available Diary data

The attack rate will be derived as the total number (count) of confirmed attacks during the treatment period divided by the number of days HAE attack diary was completed. The attack rate will be calculated for each subject:

$$\text{Weekly Attack Rate} = \frac{\text{Number of Attacks} * 7}{\text{Number of days HAE Diary was completed}}$$

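### A subject who completes dosing with blank diary days and no reported attack counts as attack-free in all three versions in SAP 10.8.2, including those the table list labels as missing-data sensitivity analyses

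*SAP*

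**What the plan says.** **Attack-free status.** SAP 10.8.2 gives three versions. In version 1, "Subjects who report no attacks and discontinued before the end of the planned treatment period (day 28) are considered attack free". Version 2 leaves out subjects who discontinue early. In version 3, "Subjects who discontinue before the planned treatment period (day 28) are considered not attack free". None refers to diary completion. In SAP 16, the attack-free tables (14.2.1.16 and its entire-study counterparts, and 14.2.2.16) carry a note calling for missing=failure and missing=excluded sensitivity analyses. SAP 10.8.2 is the only place where these variants are defined. The proportion with no attacks is listed under the primary endpoint in SAP 2.2.1 and tested with Fisher's exact test in SAP 12.1.1.

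**Weekly rate.** In SAP 10.8.1 the numerator is defined by "Number of attacks is total count of attacks reported during the respective dosing period". The denominator in SAP 10.8 comes from dose dates: "Duration (days) = 28 or (Date of last dose –date of first dose+1), whichever is earlier" for the entire dosing period and "Duration (days) = 21 or (Date of last dose –date of first dose-6), whichever is earlier" for the effective period. SAP 12.1.3 lists subjects without 28 days of diary and tabulates the missing days. It then reruns the ANCOVA with the count "divided by the number of days HAE attack diary was completed", and again with blank days filled at the qualifying rate (BOCF).

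**Diary.** Protocol 11.2.2 requires an entry every day whether or not there are symptoms, with the subject "recalling whether symptoms of an HAE attack were experienced in the last 24 hours". Sites check completion on Days 1, 7, 14, 21 and 29 and may ask subjects to correct incomplete entries.

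**The concern.** Because an entry is due every day, a blank day is missing information and not an answer of no attack. Staying on drug and keeping the diary are different behaviours, and SAP 10.8.2 protects only against loss of the first. A completer with a week of blank diary and no reported attack is a success in version 1, stays in the denominator as a success in version 2, and is still a success in version 3. A reader of a table labelled missing=failure would reasonably think that such a subject had been counted as a failure.

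The analysis sets do not remove the problem. The FAS (SAP 6.3) needs only some post-baseline diary data. The per-protocol set (SAP 6.4) sets a 90% threshold on drug taken but names none for the diary.

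At stake is whether the sensitivity versions of an endpoint listed under the primary, and tested against placebo, test what their labels say.

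**Working it through.** The plan states no figure on this point: neither document gives a missing-diary rate or a minimum completeness. The number of blank days is therefore an assumption, shown at 3 and 7 days of 28.

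**Inputs.** Protocol 5.3.3.3 gives an interim placebo rate of 0.898 attacks per week and a reduction of 0.434 for all BCX7353 doses combined, so the active rate is 0.898 − 0.434 = 0.464 per week. The window is 28 days, or 4 weeks.

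**Model.** Attacks follow a Poisson process at a constant rate λ, attacks are as likely on blank days as on other days, and an attack starting on a blank day is never recovered. With m blank days:

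- probability of truly having no attack = exp(−4λ)
- probability of being scored attack-free = exp(−λ(28 − m)/7)
- shift = the second minus the first

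| Arm | Blank days | Truly attack-free | Scored attack-free | Shift |
|---|---|---|---|---|
| Active | 3 | exp(−1.856) = 15.6% | exp(−1.657) = 19.1% | 3.4 points |
| Active | 7 | 15.6% | exp(−1.392) = 24.9% | 9.2 points |
| Placebo | 3 | exp(−3.592) = 2.8% | exp(−3.207) = 4.0% | 1.3 points |
| Placebo | 7 | 2.8% | exp(−2.694) = 6.8% | 4.0 points |

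These are shifts for a subject with that many blank days. The shift in an arm's proportion is this figure times the share of subjects affected: if a quarter of an active arm had 7 blank days, 9.2 × 0.25 = 2.3 points.

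**Equal missingness does not cancel for this endpoint.** If every subject in both arms had 7 blank days, the active-minus-placebo difference would go from 15.6 − 2.8 = 12.8 points to 24.9 − 6.8 = 18.1 points.

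**Other rates.** With 7 blank days of 28 the shift is x³ − x⁴, where x = exp(−λ). It is largest at x = 0.75: 0.4219 − 0.3164 = 10.5 points. Spread of rates between subjects could move the placebo figure up, but not beyond 10.5.

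**Effective period.** If all 7 blank days fell in the 21-day window, the active shift would be exp(−0.928) − exp(−1.392) = 39.5% − 24.9% = 14.7 points before rounding, and the placebo shift exp(−1.796) − exp(−2.694) = 16.6% − 6.8% = 9.8 points.

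**Weekly rate, for comparison.** The main formula multiplies the expected rate by (28 − m)/28, so 7 blank days lower it by 25%. A subject with 3 attacks, 21 diary days and 28 dosing days has 3 × 7/28 = 0.75 per week in the main analysis and 3 × 7/21 = 1.00 with the diary-day denominator. BOCF at a qualifying rate of 1 per week gives (3 + 1) × 7/28 = 1.00. If missingness is equal across arms, the percent reduction against placebo is unchanged.

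**The case against.** Four points on the other side carry weight.

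1. **The rate is already examined.** SAP 12.1.3 tabulates the blank days and reruns the rate in two ways, for both dosing periods and both populations. A reader might infer that the dosing-day denominator is an error and that the diary-day version must become the main rate. The documents do not support that. Which version leads is a judgement: a diary-day denominator overstates the rate if subjects skip symptom-free days or if attacks are recovered later. Results from Parts 1 and 2 are also already unblinded (Protocol 5.3.3.3 and 5.4.1.1), so a change of main definition would follow sight of the data. This stands.

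2. **Blank days would be visible.** The missing-diary listing would show who is affected, so it goes too far to say that nothing would reveal the problem. This stands, but a listing does not change how those subjects are classified, and the two reruns apply to the rate only.

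3. **A blank day need not hide an attack.** Entries can be corrected, and Protocol 5.1 describes symptoms subsiding over 3 to 5 days, so an attack beginning on an isolated blank day may be reported at the next entry. This stands. At the stated rates the shifts are upper bounds as regards recovery.

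4. **The table note may already be meant to cover diary gaps.** Possibly, but SAP 10.8.2 ties both variants to discontinuation. The two need to be reconciled.

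A reader might also take the chance of an attack falling in 7 blank days (1 − exp(−0.464) = 37% active, 1 − exp(−0.898) = 59% placebo) as the error in the attack-free proportion. It is not. Misclassification also needs no reported attack on the observed days: 0.249 × 0.371 = 9.2 points and 0.068 × 0.593 = 4.0 points.

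**Conclusion.** The gap is real for attack-free status and limited in size. As written, none of the three versions reclassifies a completer with unrecovered blank diary days and no reported attack, and the table labels suggest otherwise. For the 28-day window the shift is up to about 9 points (active) and 4 points (placebo) at 7 blank days, and about 3.4 and 1.3 points at 3, for each subject affected. This rests on the Poisson model, the interim rates, attacks being no more likely on blank days than on others, and an assumed number of blank days. If diaries are nearly complete after site review, the effect is negligible.

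The documents do not state in words that blank days are attack-free; this follows from the definitions. They do not show that diaries were poorly kept or that completion differed by arm. The weekly rate shares the feature but has adequate sensitivity analyses. With no formal hypotheses planned (Protocol 13.2.4), this is an inexpensive correction worth making before database lock, not a threat to the main result.

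**What to change.** In SAP 10.8.2, keep version 1 as the main definition. Extend version 2 (excluded) and version 3 (not attack-free) so that, besides discontinued subjects, they apply to any subject with no reported attack who still has blank diary days in the analysis window after site rectification. State this under the notes to Tables 14.2.1.16 and 14.2.2.16 so that label and definition agree. Keep the main weekly rate and report the diary-day result (Tables 14.2.1.11 and 14.2.2.11) beside it. SAP 10.8.3 should also say whether a blank day can count as an attack-free day.

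The cost is one added condition, using diary data that SAP 12.1.3 already requires to be tabulated. The downside is that both sensitivity versions become more conservative. The excluded version would drop no-attack subjects with blank days while keeping subjects with blank days who reported an attack, so it leans low. In a small arm it also loses precision: one exclusion among the 6 subjects planned at 62.5 mg in Part 3 is 1/6, or 17% of the arm. Version 1 stays the main result, so these costs fall only on the sensitivity analyses.

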## **10. STUDY CONDUCT**

### **10.1. Overview**

This is a randomized, placebo-controlled study. A subject's participation in this study is expected to be up to 65 days (inclusive of the screening and follow-up periods). Each eligible subject who consents to participate in the study will receive either 28 days of BCX7353 or placebo. All subjects will undergo a screening period of up to 21 days and a 16-day follow up period. During the 28-day dosing period, all subjects will be required to attend 6 visits: Day 1, Day 14 (safety, PK, and PD assessments), Day 7 and 21 (liver function assessment, AE, concomitant medication and diary compliance assessments), Day 15 (24-hour PK visit), and a final visit on the day following cessation of dosing, Day 29. All subjects will return for a follow-up visit on Day 44.

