All screening procedures are outlined in [Table 3](#) and are described in [Section 11](#). Subjects will be given a subject HAE attack diary, and instructed how to record details of any angioedema attacks that occur ([Section 11.2.2](#)). Subjects will be asked to complete the diary once each day starting at the screening visit.

If a subject does not initiate treatment within the 21 day screening window, all or part of the screening procedures may be repeated if the subject's medical condition has changed, at the discretion of the Investigator, following discussion with the Sponsor.

Rescreening of ineligible subjects, where there is a reasonable expectation that the subject will become eligible, will be approved or denied on a case-by-case basis with the Sponsor. Any screening ECGs may be repeated if the results suggest operator or machine error. Retesting of specific laboratory tests within the screening period without entirely rescreening a subject is permitted.

A reason for screen failure will be recorded in the screening eCRF for all subjects that do not enter the study.

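### The screening-to-baseline attack rate (SAP 10.8.1) divides by a day on which no attack can be counted, so this descriptive rate is always too low

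*SAP*

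**What the plan says.** SAP 10.8.1 defines weekly attack rates before and after treatment as well as during it. For the rate from screening to baseline, the count is defined by "Attacks with a start date after screening and before the date of first dose will be included" and the divisor by "the duration of the reporting period is date of first dose – date of screening visit+1".

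The protocol bears on this in two places. Section 10.1 limits the length: "All subjects will undergo a screening period of up to 21 days and a 16-day follow up period". Section 10.3.1 says when recording begins: "Subjects will be asked to complete the diary once each day starting at the screening visit".

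The rate is reported in Table 14.1.5.5, beside the two qualifying rates, and in Table 14.2.3.17, beside the qualifying and post-treatment rates.

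**The concern.** A rate is sound only if its numerator and denominator cover the same days. Here the count stops before the first-dose date, while the divisor runs through it. The other end is unclear. Attacks must start after screening, which may mean after the visit or after the whole of that calendar date, yet the divisor includes that date in full.

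The screening rate is the only pre-treatment rate taken from the study diary. The qualifying rate comes from historical records (Protocol 8.2.1, criterion 4). A reader who wants to know how much attack rates had already fallen before dosing, and how much further they fell on placebo or active drug, would look at the screening rate. A downward error in it moves part of any on-treatment fall into the pre-treatment period.

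**Working it through.** **Inputs**
- D = date of first dose minus date of screening visit.
- Divisor: D+1 days (SAP 10.8.1).
- Scheduled maximum: D=21. Screening runs from Day -21 to Day -1 (Protocol Table 3), there is no Day 0, and first dose is on Day 1.
- Minimum D: not stated. D=7 and D=14 below are assumptions that show the range.

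**The plan's own day counts.** Protocol 10.1 gives a total participation of 65 days, and 21 + 28 + 16 = 65, so the longest screening counts as 21 days. For that subject the SAP divisor is 21 + 1 = 22. By contrast, the dosing periods in SAP 10.8 come out as labelled for a last dose on Day 28: 28 - 1 + 1 = 28 and 28 - 1 - 6 = 21.

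**Days on which an attack can be counted**
- Reading A, screening date counted after the visit: screening date to the day before first dose, D dates.
- Reading B, screening date excluded: D-1 dates.

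**Shortfall.** For N counted attacks the SAP rate is 7N/(D+1).
- Reading A: the matched rate is 7N/D, the ratio is D/(D+1) and the shortfall is 1/(D+1).
- Reading B: the matched rate is 7N/(D-1), the ratio is (D-1)/(D+1) and the shortfall is 2/(D+1).

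| D | Divisor | Reading A | Reading B |
|---|---|---|---|
| 21 | 22 | 1/22 = 4.5% | 2/22 = 9.1% |
| 14 | 15 | 1/15 = 6.7% | 2/15 = 13.3% |
| 7 | 8 | 1/8 = 12.5% | 2/8 = 25.0% |

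These ratios concern the divisor alone and are exact for any subject with at least one counted attack. A subject with none has a rate of zero either way. At D=1, reading B leaves no countable date, so the rate is zero by construction.

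**Effect on the comparisons.** SAP section 5 expects a baseline of 1 attack/week and a placebo reduction of up to 30%, that is 0.7/week. Suppose the true screening rate equals a qualifying rate of 1/week.
- D=21, reading A: the reported screening rate is 21/22 = 0.955. An apparent fall of 4.5% from qualifying appears where there was none. The fall from screening to placebo treatment reads 1 - 0.7/0.955 = 26.7% instead of 30%.
- D=21, reading B: the reported rate is 20/22 = 0.909, and the fall to treatment reads 1 - 0.7/0.909 = 23.0%.
- D=7 (assumed): the reported rates are 0.875 (A) and 0.75 (B), and the falls read 20.0% and 6.7%.

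**The case against.** **The rate is only descriptive.** This stands. SAP 10.3 makes the qualifying rate the baseline for the attack-rate endpoint. SAP 12.1.1 uses the adjusted qualifying rate as the ANCOVA covariate, and SAP 12.1.2 takes change from that same rate. The screening rate enters no specified inferential analysis, and the 28-day and 21-day dosing periods are consistent. Randomisation is within each part, and nothing in the documents suggests that screening length differs between arms. This limits the consequence but does not remove the mismatch.

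**The size depends on wording.** This also stands. Since the diary starts at the screening visit, reading A is at least as natural as reading B. A reader might infer a general error of 9% to 25%, but the documents do not give that range. Its lower end needs reading B at the longest screening, and its upper end also needs a 7-day screening that nobody states.

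**A reader might infer that a low screening rate hides regression to the mean.** It works the other way for the step where such regression would show. The fall from qualifying to screening is exaggerated. What shrinks is the later fall from screening to treatment.

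**A reader might infer that the Entire Study Period has the opposite fault.** SAP 10.8 describes that window as "Day 1 to the last HAE diary in the follow-up period" but sets "Duration (days) = Date of last HAE Attack Diary collection during the follow-up –date of first dose", with no +1, whereas the Entire Dosing Period has "Duration (days) = 28 or (Date of last dose –date of first dose+1), whichever is earlier". The documents do not support calling this an error. SAP 10.6 ends the dosing period 24 hours after the last dose, and the +1 supplies that extension. The post-treatment period starts at last dose plus 24 hours, so to a Day 44 visit it lasts 44 - 29 = 15 days. Then 28 + 15 = 43 = 44 - 1, which is what the Entire Study Period formula gives. Counting 44 inclusive days instead would change the rate by 44/43 - 1 = 2.3%, but that is a choice of convention.

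**Conclusion.** The mismatch is real on every reading, because the first-dose date is in the divisor and never in the count. The screening-to-baseline rate is too low by 1/(D+1) or 2/(D+1), depending on whether screening-date attacks count. At the 21-day maximum that is 4.5% or 9.1%, and shorter screening makes it larger. The figures for 7 and 14 days rest on assumed lengths. Protocol 10.3.1 also lets screening be repeated or spread over several visits, so D depends on which visit date is used.

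The consequence is modest. It distorts a descriptive pre-treatment rate by an amount that differs between subjects, and hence the comparison of qualifying, screening and on-treatment rates. It does not touch the primary endpoint, the covariate or any treatment comparison. The Entire Study Period duration is consistent with the SAP's other periods and needs no correction.

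**What to change.** In SAP 10.8.1, count attacks that start after the screening visit, including later on the screening date, and before the date of first dose. Set the duration to the date of first dose minus the date of the screening visit, with no +1. Count and divisor then cover the same D dates, the 21-day maximum gives 21, and attacks on the first-dose date stay with the dosing period. Removing two days instead (D-1) would discard diary data from the screening date and give a zero divisor at D=1.

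State also which date applies when screening takes more than one visit, and whether a screening-date attack with no recorded start time counts, since SAP 10.1 would set it to noon.

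The cost is one formula and one sentence. The diary data already exist, and SAP 11.3 allows computational algorithms to be refined. Tables 14.1.5.5 and 14.2.3.17 and Listing 16.2.6.5 would use the corrected rate.
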